3.3 Safety Endpoints

1. Frequency of major bleeding^{12,13} within 72 hours of initiating treatment with the EkoSonic® Endovascular System, as defined by:
 - a. Fatal bleeding, and/or
 - b. Symptomatic bleeding in a critical area or organ, such as intracranial, intraspinal, intraocular, retroperitoneal, intraarticular or pericardial, or intramuscular with compartment syndrome, and/or
 - c. Bleeding causing a fall in hemoglobin level of 20 gL^{-1} (1.24 mmol L^{-1}) or more, or leading to transfusion of two or more units of whole blood or red cells.
2. Rate of symptomatic pulmonary embolism (PE; diagnosed using computed tomography pulmonary angiogram (CTPA), single positron emission computed tomography (SPECT), ventilation-perfusion (VQ), etc.) during hospitalization for study procedure.

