4.1.2 Exclusion Criteria

Subjects with any one of the following shall be excluded from participation in this clinical trial:

1. Treated with mechanical thrombectomy within 2 weeks of the study thrombolysis procedure.
2. Treated with thrombolysis drugs within 48 hours of the study thrombolytic procedure.
3. Life expectancy less than 1 year.
4. Body Mass Index (BMI) >40 kg/m² or per Investigator's discretion subject is able tolerate the procedure and be compliant with post-procedure increased physical activity.
5. No flow in popliteal vein on duplex imaging
6. Isolated iliac vein only thrombus.
7. Thrombus extending \geq 3 cm into the inferior vena cava (IVC). If central venous occlusion, consider computed tomography (CT) or magnetic resonance venography (MRV). For subjects with bilateral DVT, it is recommended that central imaging be performed prior to treatment to evaluate the status of the IVC.
8. Active bleeding, recent (< 3 mo) gastrointestinal (GI) bleeding, active peptic ulcer, severe liver dysfunction, bleeding diathesis.
9. Recent (< 3 mo) internal eye surgery or hemorrhagic retinopathy; recent (< 10 days) major surgery, cataract surgery, trauma, cardiopulmonary resuscitation (CPR), obstetrical delivery, or other invasive procedure.
10. History of stroke or intracranial/intraspinal bleed, tumor, vascular malformation, aneurysm.
11. Active cancer (metastatic, progressive, or treated within the last 6 months). Exception: subjects with non-melanoma primary skin cancers are eligible to participate in the study.
12. Hemoglobin < 9.0 mg/dl within 24 hours prior to the procedure
13. International normalized ratio (INR) \geq 1.5 ng/dl within 24 hours prior to the procedure
14. Platelet count < 100,000 cells/mm³ or >700,000 cells/mm³ within 24 hours prior to the procedure.
15. Creatinine outside the normal range for the treating institution and considered clinically significant by the Investigator.
16. Uncontrolled hypertension, defined as systolic \geq 175 mmHg and a diastolic \geq 110 mmHg.
17. Use of clopidogrel, ticlopidine, or other thienopyridine antiplatelet drug within 7 days of the study procedure.
18. In the judgment of the clinician, the subject is at high risk for catastrophic bleeding.
19. Known allergy, hypersensitivity, or thrombocytopenia from heparin, alteplase (rt-PA), or iodinated contrast except for mild-moderate contrast allergies for which steroid pre-medication can be used.

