4.2.2 Pre-EkoSonic® Study Treatment Procedure

Anticoagulation therapy with enoxaparin sodium (1 mg/kg twice a day) shall be initiated at least 48 hours prior to initiation of study treatment. See Appendix D and Section 4.3 Concomitant Medications for specific guidance on anticoagulation management. Hemoglobin, INR, and platelet count must be obtained within 24 hours prior to the EkoSonic® Treatment procedure in order to confirm eligibility.

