Alteplase infusion shall be started at 0.5-1.0 mg per hour, with coolant (e.g. saline) infusing at 35-120 ml/hr as the subject will tolerate. Any commercially available formulation of alteplase may be used. See Appendix C for specific thrombolytic infusion guidelines.

NOTE: A saline infusion should be connected to the side port of the introducer sheath to place the IDDC and/or angioplasty balloon. Heparinization of this infusion is not necessary as the subject will be on enoxaparin during the infusion.

Thrombolytic infusion shall be planned for at least 12 hours and overnight as needed up to a maximum of 48 hours. The EkoSonic® Device is designed to provide optimum acoustic output during the first 24 hours of operation. If the device is to be run for longer than 24 hours, a new MSD should be placed. The alteplase dose may be adjusted per Investigator discretion but should not exceed 1 mg/hour for the infusion rate and a total dose of 48 mg. The subject shall return to the nursing floor with orders to place pneumatic compression boots (PCB) on both legs during the infusion procedure. Weight based enoxaparin BID injections shall continue throughout the interventional procedure.

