5.9 Adverse events related to alteplase and definition of major bleeding

AEs related to alteplase are well-described and consist mainly of bleeding complications, including major and intracranial hemorrhage. The incidence of these complications has been quantified in subjects receiving comparatively large systemic doses of alteplase for acute myocardial infarction, stroke, and acute pulmonary embolism. Any bleeding that is attributable to alteplase is most likely to occur within 24 hours of treatment and is very unlikely to occur after 72 hours. Therefore, all bleeding events that occur within 72 hours of ultrasound-accelerated catheter-directed fibrinolysis will be attributed to the use of alteplase.

The following definition of major bleeding¹² (ISTH) shall be used: As general principles, a definition of major bleeding needs to be based on objective criteria, and major bleeds are those that result in death, are life-threatening, cause chronic sequelae or consume major health-care resources. With this in mind, the Control of Anticoagulation Subcommittee recommends the following criteria for major bleeding in non-surgical subjects:

1. Fatal bleeding, and/or
2. Symptomatic bleeding in a critical area or organ, such as intracranial, intraspinal, intraocular, retroperitoneal, intra-articular or pericardial, or intramuscular with compartment syndrome, and/or
3. Bleeding causing a fall in hemoglobin level of 20 gL⁻¹ (1.24 mmol L⁻¹) or more, or leading to transfusion of two or more units of whole blood or red cells

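### Exclusion 12 gives the pre-lysis hemoglobin limit as 9.0 mg/dl, 1000 times below the evident 9.0 g/dL, so as printed it excludes nobody

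*Protocol*

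**What the plan says.** Protocol section 4.1.2, item 12, excludes a subject with "Hemoglobin < 9.0 mg/dl within 24 hours prior to the procedure". Section 4.2.2 makes this measurement an eligibility check: "Hemoglobin, INR, and platelet count must be obtained within 24 hours prior to the EkoSonic® Treatment procedure in order to confirm eligibility". Sections 4.2.1 and 8.6 repeat the requirement. None of the three gives another limit or unit.

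Elsewhere the protocol puts hemoglobin on a g/L scale. The major-bleeding safety endpoint in section 3.3, item 1c, includes "Bleeding causing a fall in hemoglobin level of 20 gL" (with the exponent that makes it grams per liter). Section 5.9, item 3, repeats it: "Bleeding causing a fall in hemoglobin level of 20 gL⁻¹ (1.24 mmol L⁻¹) or more".

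Section 4.2.3 describes what the limit protects against: alteplase for up to 48 hours, at no more than 1 mg/hour and 48 mg in total. On anticoagulation during that time it says: "Weight based enoxaparin BID injections shall continue throughout the interventional procedure".

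The next exclusion, item 13, sets its INR limit at "1.5 ng/dl within 24 hours prior to the procedure", although INR is a ratio and has no unit.

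**The concern.** A hemoglobin limit in mg/dl cannot sit on the same scale as a bleeding definition in g/L. If item 12 is taken as printed, the mandatory 24-hour measurement is compared with a threshold that no living subject could fall below. The anemia criterion before thrombolysis then does no work.

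What is at stake is a safety criterion, not the efficacy analysis. Major bleeding within 72 hours is the primary safety analysis (section 6.2.3). It counts a 20 g/L fall in hemoglobin or a transfusion of two or more units, and baseline anemia bears directly on how well a subject tolerates such a bleed. There is also a compliance aspect. Section 10.3 defines a deviation as conduct not in accordance with the protocol. On the literal text, treating a subject at 8 g/dL would not breach item 12, so a monitor would have to depart from the wording to enforce the evident intent.

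**Working it through.** **Inputs**

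- Printed limit: 9.0 mg/dl (section 4.1.2, item 12).
- Major-bleeding fall: 20 g/L, also given as 1.24 mmol/L (sections 3.3 and 5.9).
- Evident intended limit: 9.0 g/dL. This is an inference; the protocol text at hand never prints it.

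**Step 1. Is the protocol's reference scale sound?** Assume a hemoglobin monomer mass of 16.114 g/mmol (not stated in the protocol). Then 20 / 16.114 = 1.241 mmol/L, which reproduces the printed 1.24. With 16.125 g/mmol the result is 1.240. The g/L figure in the bleeding definition is therefore internally consistent, and item 12 is the figure that does not fit.

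**Step 2. Convert the limit.** Use mg/dl ÷ 1000 = g/dL, and g/dL × 10 = g/L.

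| Limit | g/dL | g/L |
|---|---|---|
| As printed, 9.0 mg/dl | 9.0 / 1000 = 0.009 | 0.009 × 10 = 0.09 |
| Evidently intended, 9.0 g/dL | 9.0 | 9.0 × 10 = 90 |

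Ratio: 90 / 0.09 = 1000.

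**Step 3. Compare with the protocol's own scale.** 20 g/L = 2 g/dL = 2,000 mg/dl, and 2,000 / 9.0 = 222.2. A subject at the printed limit would have 0.09 g/L of hemoglobin and could not lose the 20 g/L that the safety endpoint is built to detect. A subject at 90 g/L could.

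**Step 4. The same comparison in mmol/L, using the protocol's own conversion.** 1.24 / 20 = 0.062 mmol per g. Printed limit: 0.09 × 0.062 = 0.0056 mmol/L. Intended limit: 90 × 0.062 = 5.58 mmol/L.

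**Step 5. Does anything else in the protocol supply the missing floor?**

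- Exclusion 8 covers active or recent gastrointestinal bleeding, peptic ulcer, liver dysfunction and bleeding diathesis.
- Exclusion 18 rests on the clinician's judgment of catastrophic bleeding risk.
- Exclusion 20 rests on the investigator's judgment of acute illness and comorbidity.
- Inclusion 5 (section 4.1.1) requires medical eligibility for thrombolytic drugs and points to the alteplase package insert in Appendix B.

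None of these states a hemoglobin value in the text at hand. The appendices are not shown, so nothing is claimed about them.

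**Item 13.** Removing the unit leaves the INR limit at 1.5. There is no numeric effect.

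**The case against.** The best case on the other side is that the slip corrects itself. A limit that no living subject could meet leaves one plausible reading, g/dL, and the investigators are clinicians at United States sites who will have the laboratory hemoglobin in front of them. The number 9.0 is not disputed, only its label. The INR limit in the next line carries the same kind of slip, which points to careless typing of units and not to a badly chosen threshold. Inclusion 5 and exclusions 8, 18 and 20 also require separate judgments on bleeding risk and fitness for lysis. Finally, the factors of 1000 and 222 describe one slip in different ways. The second divides a fall by a level, so it shows the scale but measures no harm.

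Most of this stands. Practical risk is low, no mis-enrolment is shown, and the ratios demonstrate the error without measuring its consequence. It is a unit error in a criterion, not a faulty calculation in the statistical plan. Two things remain. The items differ in kind: INR has no unit, so deleting the wrong one changes nothing, whereas the unit in item 12 determines what the threshold is. And the other criteria rest on history or judgment, so item 12 is the only numeric limit in the text at hand with which the mandatory hemoglobin result can be compared.

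**Conclusion.** The concern holds. As printed, the hemoglobin exclusion is 0.09 g/L against an evident 90 g/L, an error of a factor of 1000, and it excludes nobody. That the unit is wrong follows from the protocol's own 20 g/L bleeding definition. That g/dL was meant is an inference, though the only plausible one, and the sponsor should confirm it.

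The point should be corrected because it is an operative safety threshold before thrombolysis under anticoagulation. It should not be weighed as a threat to the results: no endpoint, success rule, sample size or power figure depends on it, and the document neither shows nor rules out that an anemic subject was enrolled because of it. The INR unit is a clerical slip only.

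**What to change.** After the sponsor confirms the unit, state the limit in section 4.1.2, item 12, as hemoglobin below 9.0 g/dL (90 g/L), keeping the 24-hour window. Giving both units ties it to the g/L scale of sections 3.3 and 5.9. In the same edit, delete the concentration unit from the INR limit in item 13.

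Then check any eligibility form or data-capture rule that copies either item. Section 6.2.5 reports that the interim futility analysis has already been done, so subjects have been treated. A listing of pre-procedure hemoglobin values below 9.0 g/dL would show whether the slip had any effect.

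The cost is one unit correction, one deletion, a form check and a short listing from data the protocol already requires. No analysis has to change.

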4.2 Procedures

4.2.1 Screening/Baseline Evaluation

All subjects presenting for evaluation and treatment of chronic lower extremity venous obstruction after DVT will be considered for the study. The date of evaluation will be captured along with whether the subject was included in the study or the reason for exclusion.

All subjects that meet the study's inclusion criteria and do not meet any exclusion criteria are eligible for this study. Subject Informed Consent shall be obtained prior to performing study related procedures. No subject will be enrolled without signing the Subject Informed Consent. A subject who was screened but was not eligible for the trial will be considered a screen failure. The site will maintain a log that includes each screen failure subject along with the reason for study exclusion.

EKOS will ensure that the confidentiality of subjects' identification is maintained and medical records are protected. A unique subject identification (ID) will be assigned by the data collection system for each subject enrolled in the clinical study. Subject records may be reviewed by EKOS representatives to verify the quality of the reported data; however, confidentiality will be maintained.

The following assessments shall be performed within 60 days prior to the study procedure:

- Imaging (duplex ultrasound or venography) to confirm presence of chronic DVT causing restrictive flow as well as some degree of flow in the popliteal vein. A subject who does not meet the imaging criteria will be considered a screen failure.

The following assessments shall be performed within 30 days prior to the study procedure:

- Demographics
- Pregnancy test for women of child bearing potential
- Medical history and risk factors, including any coagulopathies
- Physical exam with documentation of PTS signs and symptoms
- Villalta scale (both legs)
- CEAP classification (both legs)
- VCSS (both legs)
- SF-36
- VEINES-QOL
- Laboratory tests: hemoglobin, INR, and platelet count must be obtained within 24 hours prior to the EkoSonic® Treatment procedure in order to confirm eligibility.
- Leg circumference (both legs)

Subjects with bilateral DVT may be enrolled, so long as the study limb(s) meet inclusion/exclusion criteria, including IVC patency. If one limb meets enrollment criteria and the other does not, the limb which does not meet enrollment criteria cannot be treated until the subject is off-study. It is recommended that in a subject with bilateral DVT, central imaging be performed prior to treatment to evaluate the status of the IVC. Only one limb may be treated at a time, separated by a minimum of 30 days. Each limb will be evaluated separately and appropriately through 90 days, in accordance to the Schedule of Assessments. Subjects may have both limbs evaluated at the same visit at 180 days, and 365 days Post- EkoSonic® Study Treatment Procedure rather than separate visits for each limb.

4.2.2 Pre-EkoSonic® Study Treatment Procedure

Anticoagulation therapy with enoxaparin sodium (1 mg/kg twice a day) shall be initiated at least 48 hours prior to initiation of study treatment. See Appendix D and Section 4.3 Concomitant Medications for specific guidance on anticoagulation management. Hemoglobin, INR, and platelet count must be obtained within 24 hours prior to the EkoSonic® Treatment procedure in order to confirm eligibility.

4.2.3 EkoSonic® Study Treatment Procedure

The access site is determined by the extent of occlusive disease. When treating a single limb at a time, access via the popliteal vein is reasonable.

Once venous access has been achieved, baseline venography shall be obtained following the guidelines provided in the Venographic Imaging Manual of Operations and Procedures. Confirm presence of chronic DVT causing restrictive flow as well as some degree of flow in the popliteal vein.

Standard catheter and wire techniques are to be utilized to cross the chronic, occlusive clot. Techniques used to cross the occluded segments may include the use of a stiff Glidewire (Terumo Interventional Systems, Somerset, NJ), sharp recanalization, and chronic total occlusion catheters and wires. If a wire can be passed but not the diagnostic catheter, then serial dilatation may be used to create some "working space." Support for better pushability can be obtained by using a graduated system, such as a 4F tibial sheath coaxially through a 6F standard sheath placed through an 8F sheath.

If the occlusion cannot be crossed by the guidewire or EkoSonic® Device or there is severe vessel damage that could be further complicated by thrombolysis, such as perforation, the procedure shall be abandoned and considered a technical failure. The FTC subject shall be followed through 365 days.

Once the occlusion has been successfully crossed, balloon dilatation of the chronic clot shall be performed to create working space and to macerate/crack the hard thrombus. Vessels to be dilated should be sized for appropriate balloon sizing. Example guidelines are: 12-16 mm for IVC, 10-12 mm for iliac veins, 8-10 mm for femoral veins and 6-8 mm for popliteal veins. Cracking the chronic clot may allow for better penetration of alteplase. Once venoplasty has been performed throughout the entire diseased segment, venography imaging shall be obtained prior to placement of the IDDC. Care should be taken to obtain the same images as obtained at baseline venography.

An EkoSonic® IDDC with the treatment zone length selected to cover the entire occlusive segment is placed over the guide wire. The guide wire is then removed and the MSD inserted into the IDDC and luer locked in place. See Appendix C for specific guidance on EkoSonic® Device selection and placement.

Alteplase infusion shall be started at 0.5-1.0 mg per hour, with coolant (e.g. saline) infusing at 35-120 ml/hr as the subject will tolerate. Any commercially available formulation of alteplase may be used. See Appendix C for specific thrombolytic infusion guidelines.

NOTE: A saline infusion should be connected to the side port of the introducer sheath to place the IDDC and/or angioplasty balloon. Heparinization of this infusion is not necessary as the subject will be on enoxaparin during the infusion.

Thrombolytic infusion shall be planned for at least 12 hours and overnight as needed up to a maximum of 48 hours. The EkoSonic® Device is designed to provide optimum acoustic output during the first 24 hours of operation. If the device is to be run for longer than 24 hours, a new MSD should be placed. The alteplase dose may be adjusted per Investigator discretion but should not exceed 1 mg/hour for the infusion rate and a total dose of 48 mg. The subject shall return to the nursing floor with orders to place pneumatic compression boots (PCB) on both legs during the infusion procedure. Weight based enoxaparin BID injections shall continue throughout the interventional procedure.

4.2.4 Post-EkoSonic® Procedure

The following assessment should be performed immediately after the completion of the EkoSonic® Procedure.

- Venography

Adjunctive therapy may then be considered, as necessary. Stenting across the inguinal crease is only considered when there is poor flow from the femoral vein into the common femoral vein (CFV) and iliac veins, and all other measures have been exhausted. If stenting is necessary, IDEV Supera 8 mm stent is recommended for crossing of the inguinal ligament and CFV. If adjunctive therapy is performed, the following assessment should be performed immediately following the procedure.

- Venography

Upon completion of study treatment, the catheter and sheath shall be removed and hemostasis obtained with pressure over the insertion site followed by placement of a pressure dressing. PCB shall remain placed on both legs until hospital discharge. Anticoagulation therapy with weight based enoxaparin sodium shall also be continued through discharge (see Concomitant Medication section below). The following assessments should be performed following the completion of study treatment.

- Duplex imaging (within 24 hours of the completion of treatment)
- Laboratory tests (within 24 hours of the completion of treatment)
- Adverse Events

4.2.5 Discharge

The subject shall be discharged with prescriptions for enoxaparin (1 mg/kg bid for 90 days) and a pair of 30 to 40 mm Hg ECS. If necessary, enoxaparin may be converted to an oral anticoagulant after 30 days (e.g. 20 mg rivaroxaban daily). Treatment with the ECS and oral anticoagulation should continue for the duration of the study.

If limb swelling and discomfort is too great for standard ECS use, leg wraps, leg elevation, and pumps can be used to reduce the swelling and pain and allow for earlier ECS use. One may also consider using 20-30 mmHg ECS if necessary. The subject shall be encouraged to ambulate and exercise early and often, as tolerated.

4.2.6 Follow-Up Visits and Early Termination

At each of the follow-up visits: **Days 30± 7 days, 90± 10 days, 180± 14 days, 365 ± 14 days and at early termination**, the following assessments shall be performed:

- Duplex imaging
- Villalta scale (both legs)
- CEAP classification(both legs)
- VCSS (both legs)
- SF-36
- VEINES-QOL
- Leg circumference (both legs)
- Review of compliance with anticoagulant therapy, ECS, and exercise
- Serious Adverse and bleeding events
- Concomitant medications

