VCSS	X				X	X	X	X	X
SF-36	X				X	X	X	X	X
VEINES-QOL	X				X	X	X	X	X
Venography		X ⁵	X ⁶						
Leg Circumference	X				X	X	X	X	X
Review of Treatment Compliance & Exercise					X	X	X	X	X
Adverse Events			X	X	X	X	X	X	X
Concomitant medications	X				X	X	X	X	X

¹ Duplex ultrasound within 60 days prior to treatment or venography (Pre- EkoSonic® Treatment) will be performed to confirm persistent chronic DVT causing restrictive flow

²To be performed within 24 hours of the completion of treatment

³Test results may be obtained within 30 days prior to study treatment, unless otherwise specified in the exclusion criteria

⁴To be performed within 24 hours prior to the start of treatment

⁵ To be performed pre- and post-venoplasty

⁶To also be performed post- adjunctive treatment

C. ACRONYMS AND ABBREVIATIONS

AE	Adverse event
aPTT	Activated partial thromboplastin time
CBC	Complete blood count
CEAP	Clinical, Etiologic, Anatomic, Pathophysiological
CFR	Code of Federal Regulations
CFV	Common femoral vein
CPK-MB	Creatine Phosphokinase-MB
CPR	Cardiopulmonary resuscitation
CT	Computed tomography
CTPA	Computed tomography pulmonary angiogram
DIC	Disseminated intravascular coagulation
DVT	Deep vein thrombosis
eCRF	Electronic Case Report Form
ECS	Elastic compression stockings
FTC	Failure-to-Cross
FDA	Food and Drug Administration
GI	Gastrointestinal
ID	Identification
IDDC	Intelligent Drug Delivery Catheter
INR	International normalized ratio
ITT	Intention-to-treat
IVC	Inferior vena cava
MDR	Medical Device Reporting
MRI	Magnetic Resonance Imaging
MRV	Magnetic resonance venography
MSD	MicroSonic Device
PCB	Pneumatic compression boots
PCS	Physical component summary
PE	Pulmonary Embolism
PP	Per protocol
PTS	Post-thrombotic syndrome
PTT	Partial thromboplastin time
QoL	Quality of Life
rt-PA	Recombinant tissue plasminogen activator
SAR	Serious adverse reaction
SAE	Serious adverse event
SF-36	Short Form 36
SPECT	Single positron emission computed tomography
VEINES-QOL	Venous Insufficiency Epidemiological and Economic Study- Quality of Life
VCSS	Venous Clinical Severity Score
VVI	Venous Volumetric Index
VQ	Ventilation-perfusion

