5.7 Documentation of adverse events

AEs shall be reported when noted during the hospitalization for the initial treatment and in the subject's medical record through the 30 day follow-up period. Subjects shall be encouraged to report AEs spontaneously or in response to non-directed questioning by their usual healthcare providers (for example, in response to the question "How has your health been since you last visit?"). If it is determined that an AE has occurred, the study staff member entering data into the eCRF should obtain all of the information necessary to complete the AE section.

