5.8 Reporting and duration of AE reporting period

Because the EkoSonic® Endovascular System is a commercial medical device, Investigators will comply with any hospital user reporting requirements. All observed or reported AEs including type of event, severity and relationship to the procedure, device use, thrombolytic and anticoagulant drug use will be recorded in the eCRF during hospitalization and through

30 day follow-up. At subsequent visits, SAEs and AEs related to venous thromboembolism or the EkoSonic® treatment will be collected.

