5.10 Specific reporting guidelines

Study Investigators should adhere to the following guidelines to ensure the quality and precision of AE reporting:

Use recognized medical terms.

Avoid the use of colloquialisms and non-standard abbreviations

If known at the time of AE reporting, a diagnosis should be reported instead of individual symptoms and signs (for example, record only “pneumonia” rather than “productive cough” and “elevated white blood cell count”).

If the reported symptoms and signs cannot be medically characterized as a single diagnosis or syndrome at the time of AE reporting, the information that is available should be reported. If a diagnosis is subsequently established, it should be reported as follow-up information as described earlier.

A cascade of clinical events (such as sequelae of an adverse event) should be identified as the primary, causative event. The cascade of events can be further described in the primary AE narrative. For example, when recording a death, the event or condition that caused or contributed to the fatal outcome should be reported as the serious adverse event. If the cause of death is unknown and cannot be determined at the time of reporting, “unknown cause of death” should be recorded as the adverse event.

Any AE potentially related to the study procedure that results in inpatient re-hospitalization or prolongs the index hospitalization (for study treatment) should be reported as a SAE. If a subject is re-hospitalized to undergo a medical or surgical procedure as a result of an AE, the event responsible for the procedure (not the procedure itself) should be reported as the SAE. For example, if a subject is re-hospitalized to undergo exploratory surgery as a result of a major bleeding event, record the major bleeding event that necessitated surgery as the SAE.

All observed or reported serious bleeding events occurring through the 365 day follow-up period, must be recorded.

Previously scheduled hospitalizations required for diagnostic or elective surgical procedures for the management of unchanged pre-existing medical conditions shall not be considered AEs.

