5.14 Safety Monitor

A safety monitor shall review and adjudicate all SAEs and bleeding events during the study. The safety monitor will determine if the AE meets the definition of serious and unexpected and shall notify the sponsor if the number or type of events is of concern.

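### Section 4.2.6 conflicts with sections 5.7/5.8 and the Schedule of Assessments on which adverse events are collected at the follow-up visits

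*Protocol*

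**What the plan says.** Four places in the protocol bear on which events a site records at follow-up.

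- **Section 4.2.6** gives one list of assessments for Day 30, 90, 180, 365 and early termination. Its safety item is "Serious Adverse and bleeding events". Bleeding carries no seriousness limit.
- **Sections 5.7 and 5.8** set the scope by time. Section 5.7 has AEs reported during the index hospitalization and "in the subject's medical record through the 30 day follow-up period". Section 5.8 covers the same period: "All observed or reported AEs including type of event, severity and relationship to the procedure" and to other study components go into the eCRF. For later visits, 5.8 says "At subsequent visits, SAEs and AEs related to venous thromboembolism or the EkoSonic® treatment will be collected".
- **The Schedule of Assessments** has a row labelled "Adverse Events", marked post-treatment, at discharge, at all four follow-up visits and at early termination. No footnote limits it.
- **Sections 5.10 and 5.14** add two related statements. Section 5.10 says "All observed or reported serious bleeding events occurring through the 365 day follow-up period, must be recorded". Section 5.14 says "A safety monitor shall review and adjudicate all SAEs and bleeding events during the study".

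Section 6.2.3 then plans three AE tables: everything reported, events judged related, and serious events. None is given a time window.

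**The concern.** These are instructions for the same visits, and they do not ask for the same events. Section 4.2.6 is what a coordinator is likely to work from on the day. Taken literally, it does not ask at Day 30 about a non-serious, non-bleeding event since discharge, which 5.7 and 5.8 require. After Day 30 it is narrower than 5.8 in one respect and wider in another.

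This is not detail that an analysis plan could supply later, because no analysis can recover an event that was never recorded. The tables in 6.2.3 have no window of their own, so they inherit whichever scope each of the up to 30 sites applied. The study has a single arm, so under-collection would look like a lower event rate, with no control group to reveal it.

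**Working it through.** No figure is in dispute, so the check sets the scopes side by side by event class. Yes means that the text, read literally, asks for the event.

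| Window | Event class | 4.2.6 | 5.7/5.8 | Schedule row |
|---|---|---|---|---|
| Through Day 30 | Serious AE | yes | yes | yes |
| Through Day 30 | Any bleed | yes | yes | yes |
| Through Day 30 | Non-serious, non-bleeding AE | **no** | yes | yes |
| After Day 30 | Serious AE, including serious bleeds and deaths | yes | yes | yes |
| After Day 30 | Non-serious bleed linked to VTE or EkoSonic treatment | yes | yes | yes |
| After Day 30 | Non-serious bleed linked to neither | yes | **no** | yes |
| After Day 30 | Non-serious non-bleeding AE linked to VTE or EkoSonic treatment | **no** | yes | yes |
| After Day 30 | Other non-serious AE | **no** | **no** | yes |

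The texts agree on four of the eight classes and differ on the other four: one of three through Day 30 and three of five afterwards.

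**Sections 5.10 and 5.14.** Section 5.10 requires serious bleeds to Day 365. Every column already includes these, so it is a minimum and conflicts with nothing. Section 5.14 governs adjudication, not collection. It still presupposes that all bleeds reach the safety monitor, and after Day 30 section 5.8 does not require non-serious bleeds linked to neither VTE nor EkoSonic treatment.

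**Are such bleeds foreseeable?** Yes. Section 4.2.5 continues anticoagulation for the duration of the study. Section 5.12 includes anticoagulation medication in the relatedness scale, and the related-events table in 6.2.3 covers medications as well as procedure and device. A minor bleed on long-term anticoagulant could therefore belong in that table and yet fall outside 5.8.

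**Planned safety outputs against the disputed classes:**

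- Major bleeding within 72 hours of initiation: captured under every reading.
- Symptomatic pulmonary embolism during the procedure hospitalization: precedes the visits governed by 4.2.6, so unaffected.
- Deaths and the serious-event table: serious events are in every column, and 5.13 requires them to be reported throughout the study. Unaffected.
- Tables of all reported events and of related events: affected, for non-serious events only.
- Bleeds available for adjudication under 5.14: affected after Day 30, for non-serious bleeds linked to neither VTE nor EkoSonic treatment.

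**The case against.** The best defence is that a careful site would read the sections together. Section 5.8 is the dedicated statement of the reporting period, 4.2.6 is one line in a checklist, and the Schedule row prompts for AEs at every visit. Section 5.15 provides a common data capture system, site training and periodic review of inconsistent data. The eCRF is not shown and may already prompt for the wider scope.

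Much of this stands. It means that sites could miss events, not that they will, and that uneven capture across sites is a risk and not a demonstrated fact. It does not remove the contradiction: the protocol nowhere says which text prevails or that the scopes are to be combined. Data review can query an inconsistent entry but is unlikely to find an event that nobody asked about.

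A reader might infer more than the document supports:

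- **That five sections give five competing rules.** Sections 5.7 and 5.8 agree, 5.10 is a minimum and 5.14 concerns adjudication.
- **That 4.2.6 and 5.8 are mirror images after Day 30.** Section 5.8 still captures every serious bleed and any bleed linked to VTE or EkoSonic treatment.
- **That planned counts of late bleeding or recurrent thrombosis are compromised.** Section 6.2.3 plans no separate count of either. Re-occlusion is assessed by duplex, and revascularizations have their own case report form (4.6).
- **That AE recording should start with enoxaparin, which under 4.2.2 "shall be initiated at least 48 hours prior to initiation of study treatment".** This is a preference about the start date, not a conflict between texts at the same visit. Serious events are already reportable throughout the study, and the Safety Subject Set begins at attempted venous access. Inclusion criterion 7 requires prior therapeutic anticoagulation, and section 4.3 transitions only subjects not already on enoxaparin. For those already taking it, a first protocol-directed dose cannot be identified.

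**Conclusion.** The contradiction is real and minor. At Day 30, 4.2.6 is narrower than 5.7/5.8. After Day 30, 4.2.6, 5.8 and the Schedule row give three different scopes, and the adjudication duty in 5.14 assumes bleeds that 5.8 does not require. Three omissions matter:

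- non-serious non-bleeding AEs up to Day 30, if a site follows 4.2.6;
- non-serious non-bleeding AEs linked to VTE or treatment after Day 30, if it follows 4.2.6;
- non-serious bleeds linked to neither after Day 30, if it follows 5.8.

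The fourth disputed class, other non-serious AEs after Day 30, is requested only by the unrestricted Schedule row.

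The consequence is limited to two descriptive tables and the bleeds put to the safety monitor. A reader should not take this as a threat to the primary safety analysis or to the death and serious-event summaries. The conclusion rests on reading each text literally and on the absence of a stated order of precedence. If the eCRF already prompts for the combined scope, the practical loss may be small; the protocol does not allow it to be counted.

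**What to change.** Replace the safety line in 4.2.6 with one scope per time window, drawn from what the sections already ask for:

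- **Through Day 30:** all AEs.
- **After Day 30 to Day 365:** serious AEs, all bleeding events whatever their seriousness, and AEs linked to VTE or EkoSonic treatment.

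Then align the related text:

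- Section 5.8: add all bleeding events to the post-Day-30 rule. Section 5.7 already matches the first window.
- Section 5.10: ask for all bleeding events to Day 365, so that the safety monitor receives what 5.14 says will be adjudicated.
- Schedule of Assessments: add a footnote to the AE row giving the two windows.
- Section 6.2.3: state the window for each AE table, so that tables of all reported and of related events do not mix periods with different collection rules without saying so.

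No change to the start of AE recording is needed. The cost is protocol wording, eCRF prompts and slightly more AE entry.
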